**EGSS Missing Data Imputation**

A similar procedure will be used for the analyses based on percentage of EGSS successes wherein the ANCOVA analysis is replaced with a logistic regression analysis. Specifically, missing 12 week EGSS values from which the dichotomized EGSS is derived will be estimated by MCMC which does not rely on the assumption of data missing at random. Additionally, the pattern of missing observations in each treatment group cannot influence the missing value estimation in the other because the imputation is being conducted independently for each treatment group.

The missing 12-week EGSS values will be derived for the analysis using the method of Markov Chain Monte Carlo (MCMC) multiple imputation. Multiple imputation and subsequent analysis will involve 3 principal tasks:

1. Create a data set, one for each treatment group, of subjects with observed values and those needing estimation by MCMC. The missing EGSS values in each data set will be filled in using the MCMC method 5 times to generate 5 data sets. The resulting data sets for each treatment arm will be combined into one complete data set by imputation.

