### 12.1.6 Statistical Hypothesis Testing and Control of Multiplicity

Statistical hypothesis testing for lesion count analyses will use the statistical model introduced in Section 12.1.4 and employs the methods of Section 12.1.9 regarding missing values. The analysis of the dichotomized Evaluator’s Global Severity Score will be based on the logistic regression with factors of treatment group and analysis center and employs the methods of Section 12.1.9 regarding missing values.

The overall Type I error will be controlled by requiring the three co-primary efficacy endpoints to be statistically significant. Specifically, failure of any one of the primary efficacy endpoints will invalidate the statistical significance of the secondary efficacy endpoints.

The following stepwise process will be conducted for testing the secondary efficacy endpoints in order to control for multiplicity. These tests will be performed for only the ITT population. The testing process will terminate whenever a statistical test for a step is not significant. All subsequent tests for the remaining steps will be considered not significant. The order of testing is:

Step Number	Secondary Endpoint
1	Percent change in non-inflammatory lesion count from Baseline to Week 12
2	Percent change in inflammatory lesion count from Baseline to Week 12
3	Percentage of subjects who have at least a 2 grade reduction at Week 12 from Baseline in the Evaluator’s Global Severity Score
4	Percent change in non-inflammatory lesion count from Baseline to Week 8
5	Percent change in inflammatory lesion count from Baseline to Week 8
6	Percent change in non-inflammatory lesion count from Baseline to Week 4
7	Percent change in inflammatory lesion count from Baseline to Week 4

The following stepwise process will be conducted for testing the supportive efficacy endpoints in order to control for multiplicity. These tests will be performed for only the ITT population. In order to control for multiplicity, failure of any one of the secondary efficacy endpoints will invalidate the statistical significance of the supportive efficacy endpoints. The testing process

will terminate whenever a statistical test for a step is not significant. All subsequent tests for the remaining steps will be considered not significant. The order of testing is:

Step Number	Supportive Endpoint
1	Percent change in non-inflammatory lesion count from Baseline to Week 2
2	Percent change in inflammatory lesion count from Baseline to Week 2

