### **12.1.9 Missing Efficacy Data Imputations**

#### *Lesion Count Variable Missing Data Imputation*

Missing 12 week data will be estimated by multiple imputation and subsequently analyzed. Missing lesion count data will be derived for the analysis using the method of MCMC multiple imputation which does not rely on the assumption of data missing at random. Additionally, the pattern of missing observations in each treatment group cannot influence the missing value estimation in the other because the imputation is being conducted independently for each treatment group.

Multiple imputation and subsequent analysis will involve 3 distinct phases with these principal tasks:

1. Create a data set of subjects, one for each treatment group, with observed values and those needing estimation by MCMC. The missing lesion count values in each data set will be filled in using the MCMC method 5 times to generate 5 data sets. The resulting data sets for each treatment arm will be combined into one complete data set for each imputation.

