**Syntax:**

```
proc mi data=datain out=dataout seed=&seed. nimpute=5 <options>;
  where trtpn=(1, or 2);
```

```

mcmc chain=multiple;
var baseline week2 week4 week8 week12;
run;

```

2. For each complete data set, the dichotomous success rate (clear or almost clear with a 2-point change from baseline) will be computed. The 12-week imputed EGSS values will be rounded to the nearest integer value prior to evaluating the success rate. Each complete data set will be analyzed with a logistic regression with factors of treatment group and analysis center.
4. The results from these analyses will be combined into a single inference using SAS PROC MIANALYZE.

A total of 2 random seeds will be needed to impute EGSS for the two treatment groups. Those 2 random seeds have been pre-specified by using a random number generator:

- EGSS; IDP-120 Gel: Seed= 923694678
- EGSS; IDP-120 Vehicle: Seed= 802843905

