### 12.1.10 Sensitivity Efficacy Analyses

#### Sensitivity analyses for absolute change in lesion count

The first sensitivity analysis for absolute change in lesion count will use a repeated measures ANCOVA, with treatment, analysis center, and visit (ie, Week 4, Week 8) as independent factors and a covariate of baseline lesion count. In this analysis, data from all post-baseline visits will be included with no imputation for missing data.

The second sensitivity analysis will use the model based multiple imputation method to impute missing data for the absolute change in lesion counts at Week 12. Although the full details will be presented in the SAP, the multiple imputation will involve 3 principal tasks:

1. Missing values will be filled in 5 times to generate 5 data sets. The imputation model used will be an ANCOVA with factors of treatment group and analysis center, and a covariate of baseline lesion count (ie, the imputation model will be the same as the analysis model). Appropriate modifications will be made should the analysis be based on a non-parametric method.
2. Each complete data set will be analyzed with an ANCOVA with factors of treatment group, and analysis center, and a covariate of baseline lesion count.
3. Results from these analyses will be combined into a single inference using SAS PROC MIANALYZE.

A total of 2 random seeds will be needed. Those 2 random seeds have been pre-specified by using a random number generator:

- Inflammatory Lesion Counts: Seed= 1792696133
- Non-Inflammatory Lesion Counts: Seed= 1438330601

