### **12.8.2 Sample Size Determination**

These power calculations are based primarily on the observed Week 12 results of the Phase 2 study, V01-120A-201. This study was a four-arm trial including IDP-120 Gel versus its individual gel components and Vehicle Gel and is therefore a relevant study for powering the current study.

A sample size of 300 per treatment arm has greater than 99% power to detect a statistically significant difference in non-inflammatory lesions with a significance level of 0.05. The estimated absolute change from baseline in treatment means were 13.3 and 8.7 for IDP-120 Gel versus its Vehicle gel, respectively, with a standard deviation of 11.0.

A sample size of 300 per treatment arm has greater than 99% power to detect a statistically significant difference in non-inflammatory lesions with a significance level of 0.05 using the estimated absolute change from baseline in treatment means of 18.8 and 7.8 for IDP-120 Gel versus its Vehicle Gel, respectively, with a standard deviation of 16.4.

In order to achieve at least 95% power to detect a statistically significant difference in the percentage of subjects who have at least a 2 grade reduction at Week 12 from Baseline in EGSS and are Clear or Almost Clear with a significance level of 0.05, a sample size of 293 per treatment group is required. The estimated percentages with a 2 grade reduction at Week 12 from Baseline in the EGSS and Clear or Almost Clear are 26.6% and 14.3% for IDP-120 Gel versus its Vehicle Gel respectively. For simplicity, a sample size of 300 per treatment arm will be used.

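### Five imputations leave avoidable Monte Carlo noise and a small power loss, mainly in the EGSS co-primary; 100 or more removes most of both at almost no cost

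*Combined protocol and SAP*

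**What the plan says.** Section 12.1.9 makes MCMC multiple imputation, run separately by arm, the primary way of handling missing Week 12 data. For lesion counts: "The missing lesion count values in each data set will be filled in using the MCMC method 5 times to generate 5 data sets". For EGSS: "The missing EGSS values in each data set will be filled in using the MCMC method 5 times to generate 5 data sets". The EGSS code matches the text: "proc mi data=datain out=dataout seed=&seed. nimpute=5 <options>". The lesion-count code also has nimpute set to 5. Results are pooled with PROC MIANALYZE. The seeds are fixed in advance; for EGSS: "Those 2 random seeds have been pre-specified by using a random number generator".

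Section 12.1.10 uses the same number for the multiple-imputation sensitivity analyses of lesion counts and of EGSS: "Missing values will be filled in 5 times to generate 5 data sets".

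No section explains the choice of five, sets a Monte Carlo error target or gives an expected dropout rate. Section 12.8.2 has no dropout allowance beyond rounding 293 per group up to 300. On the consequence of a miss, section 12.1.6 says that "failure of any one of the primary efficacy endpoints will invalidate the statistical significance of the secondary efficacy endpoints".

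**The concern.** A pooled multiple-imputation result has two sources of variation: the sample, and the random draws used to fill in the gaps. The second can be made as small as one likes by drawing more imputations. At five it is not small, so the pooled p-value carries noise unrelated to the data. Rubin's rules pay for that noise with a wider variance and a t reference on few degrees of freedom. This protects type I error but uses up power.

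EGSS is where it matters. All three co-primaries must be significant, and EGSS has the least power in section 12.8.2. A borderline EGSS result could pass or fail because of the seed, and a failure would also end secondary testing. The repeated-measures and tipping point analyses in section 12.1.10 could show that a result is fragile, but they do not change the primary decision.

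**Working it through.** **Inputs from section 12.8.2.** 300 per arm. EGSS success: "Clear or Almost Clear are 26.6% and 14.3% for IDP-120 Gel versus its Vehicle Gel respectively". Lesion-count changes: 13.3 v 8.7 (SD 11.0) and 18.8 v 7.8 (SD 16.4). Both lesion paragraphs there are labelled non-inflammatory; I read the first as inflammatory, which does not affect the EGSS result. Alpha is two-sided 0.05 (section 12).

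**Assumed input.** FMI of 5, 10, 20 and 30%.

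**The plan's own figure.** Without continuity correction, n = [1.96·√(2·0.2045·0.7955) + 1.645·√(0.266·0.734 + 0.143·0.857)]² / 0.123² = 276.5, so 277. With correction, (276.5/4)·[1 + √(1 + 4/(276.5·0.123))]² = 292.5, so 293. This matches the stated 293 per group.

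**Expected z with complete data.**
- EGSS: log odds ratio = ln[(0.266/0.734)/(0.143/0.857)] = 0.776. Its variance is [1/(0.266·0.734) + 1/(0.143·0.857)]/300 = 0.0443, so SE = 0.210 and z = 3.69.
- Inflammatory: 4.6/(11.0·√(2/300)) = 5.12.
- Non-inflammatory: 11.0/(16.4·√(2/300)) = 8.21.

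**Effect of m imputations.** Let U be the complete-data variance, T = U/(1−FMI) the total variance at unlimited m, and B = FMI·T the between-imputation variance.
- Expected z at unlimited m is the complete-data z times √(1−FMI).
- The m-imputation estimate adds variance B/m, so its Monte Carlo SE as a share of the total SE is √(FMI/m).
- The test uses variance U + (1+1/m)·B̂, with B̂ estimated on m−1 degrees of freedom.
- The reference is t with (m−1)(1+1/r)² degrees of freedom, where r = (1+1/m)·B̂/U.

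Simulating about 1 million trials per setting gave, for EGSS:

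| FMI | 5% | 10% | 20% | 30% |
|---|---|---|---|---|
| Expected z, unlimited m | 3.59 | 3.50 | 3.30 | 3.08 |
| Monte Carlo SE / total SE, m=5 | 10.0% | 14.1% | 20.0% | 24.5% |
| Same, m=100 | 2.2% | 3.2% | 4.5% | 5.5% |
| Power, unlimited m | 94.9% | 93.8% | 91.0% | 87.0% |
| Power, m=5 | 94.6% | 93.2% | 88.8% | 82.4% |
| Power, m=100 | 94.9% | 93.8% | 90.9% | 86.8% |
| Decision differs from unlimited m, m=5 | 0.9% | 1.8% | 4.2% | 7.8% |
| Same, m=100 | 0.2% | 0.3% | 0.7% | 1.2% |
| Two seeds disagree on the same data, m=5 | 1.3% | 2.5% | 5.9% | 11.1% |
| Same, m=100 | 0.3% | 0.5% | 1.0% | 1.7% |

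Taken before rounding, the power lost to m=5 is about 0.2, 0.6, 2.1 and 4.6 points; repeat runs vary by about 0.1 point. In subjects this is about 7, 17, 43 and 73 of 600. For FMI 20%, power of 88.8% corresponds to z = 1.96 + 1.22 = 3.18, and 600·[1 − (3.18/3.30)²] is about 43.

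**Type I error.** Simulated under the null, m=5 gives 4.98 to 5.07%.

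**Lesion counts.** For the inflammatory count the m=5 decision differs in 0.04, 0.1, 0.4 and 1.4% of trials across the same FMI values. For the non-inflammatory count it never does.

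**A single data set.** Suppose FMI is 10% and p would be 0.025 at unlimited m. Over seeds, the central 90% range of p is 0.013 to 0.054 at m=5, with 7% of seeds above 0.05. At m=100 the range is 0.022 to 0.029.

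**Patient-level checks.** These imputed EGSS by arm under a normal model with rounding as in section 12.1.9, and analysed the log odds ratio without centers.
- With monotone dropout of 5, 10, 15, 20 and 30% and an assumed adjacent-visit correlation of 0.75, mean FMI was 4.6, 9.1, 13.3, 17.5 and 25.6%. Decisions at m=5 and m=300 differed in 0.7, 1.2, 2.4, 2.7 and 6.2% of 450 trials per rate.
- A separate run of 600 trials per rate, at 10, 15 and 20% dropout, gave power of 93.8 v 94.3%, 88.5 v 91.3% and 86.5 v 89.0% at m=5 v m=100.

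Both agree in direction and rough size with the table.

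**The case against.** The strongest reply is that nothing here is invalid. Type I error holds, every seed is fixed, and the verdict for given data is therefore determined and reproducible; another seed is one the plan would never use. That is right as far as validity and selection go. It does not remove the noise: the one seed that is used is still an arbitrary draw.

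The size also depends on an assumed FMI. At 5 to 10% the power loss is under one point, and the large figures need FMI near 30%, which in the patient-level check even 30% dropout did not reach. Changed decisions go both ways: at FMI 10%, 1.22% of trials turn from success to failure and 0.56% the other way, so the gross rate overstates the net harm. Borderline results are uncommon at the planned effect. At FMI 10% the median p at unlimited m is about 0.0005, and only 2.9% of trials fall between 0.02 and 0.03. All of this stands and keeps the point modest.

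Finally, 100 is not a threshold. At FMI 20%, power is 90.6% at m=20 and 90.8% at m=50, so most of the power is back well before 100. Stability gains more from going higher: at m=20 the decision still differs in about 1.6% of trials, against 0.7% at m=100. Since larger m has no statistical downside, there is little reason to stop early.

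**Conclusion.** The concern holds as a free improvement to a valid analysis. Five imputations cost EGSS about 0.2 to 2.1 points of power at FMI 5 to 20%, and 4.6 points at 30%. They change its decision in about 1 to 4% of trials over the lower range and in 7.8% at 30%. For the lesion counts the practical effect is negligible unless FMI is high. The direction is certain. The size rests on the assumed FMI and on the Phase 2 EGSS rates being true. More imputations do not abolish seed dependence: at FMI 10% and a limiting p of 0.048, 32% of seeds would still give p above 0.05 at m=100.

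**What to change.** Before unblinding, set the number of imputations to at least 100 in section 12.1.9 (the text and both PROC MI calls) and in both multiple-imputation sensitivity analyses in section 12.1.10, and carry this into the SAP. Section 12 says that the SAP will be finalized before unblinding, so there is a route for the change. Keep the pre-specified seeds.

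Preferably add a Monte Carlo error target, with the number raised if the estimated FMI requires it. One example is a standard error of the p-value of at most 0.005 when p is 0.05. At FMI 10, 20 and 30%, m=5 gives 0.021, 0.036 and 0.051, and m=100 gives 0.0041, 0.0062 and 0.0082. The target is met by m=100 at FMI 10%, m=200 at 20% (0.0044) and m=300 at 30% (0.0047). A flat 100 therefore meets it only at the lower FMI.

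The cost is a changed number and minutes of computing, with no effect on subjects, data collection or type I error. Section 12.1.4 does not say how the skewness test and the interaction rule are settled across imputed data sets. That gap already exists with five imputations and can be closed in the same edit.

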**Syntax:**

```
proc mi data=datain out=dataout seed=&seed. nimpute=5 <options>;
  where trtpn=(1, or 2);
```

```

mcmc chain=multiple;
var baseline week2 week4 week8 week12;
run;

```

2. For each complete data set, the dichotomous success rate (clear or almost clear with a 2-point change from baseline) will be computed. The 12-week imputed EGSS values will be rounded to the nearest integer value prior to evaluating the success rate. Each complete data set will be analyzed with a logistic regression with factors of treatment group and analysis center.
4. The results from these analyses will be combined into a single inference using SAS PROC MIANALYZE.

A total of 2 random seeds will be needed to impute EGSS for the two treatment groups. Those 2 random seeds have been pre-specified by using a random number generator:

- EGSS; IDP-120 Gel: Seed= 923694678
- EGSS; IDP-120 Vehicle: Seed= 802843905

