**Criteria for evaluation:****Co-Primary efficacy:**

IDP-120 Gel will be compared to IDP-120 Vehicle Gel.

Co-primary endpoints are:

- (1) Superiority in absolute change from Baseline to Week 12 in mean inflammatory lesion counts
- (2) Superiority in absolute change from Baseline to Week 12 in mean non-inflammatory lesion counts, and,
- (3) Percentage of subjects who achieve at least a two-grade reduction from baseline and are Clear or Almost Clear at Week 12 in the Evaluator's Global Severity Score.

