**Supportive Efficacy:**

- Percent change in non-inflammatory lesion count from Baseline to Week 2
- Percent change in inflammatory lesion count from Baseline to Week 2
- Percentage of subjects who have at least a 2 grade reduction at Week 8 from Baseline in the Evaluator's Global Severity Score
- Percentage of subjects who have at least a 2 grade reduction at Week 4 from Baseline in the Evaluator's Global Severity Score
- Percentage of subjects who have at least a 2 grade reduction at Week 2 from Baseline in the Evaluator's Global Severity Score

**Efficacy Measurements:***Lesion Counts*

At each visit the Evaluator will count the total number of inflammatory lesions (papules, pustules, and nodules) on the subject's face. Nodules will be counted separately but will be included in the total inflammatory lesion count. At baseline, eligible subjects may have no more than two nodules. Nodules will be included in the statistical analysis of inflammatory lesion counts. All inflammatory lesions will be counted at the same time rather than counting papules and pustules separately. The Evaluator will also count the total number of non-inflammatory lesions (open and closed comedones). The same blinded evaluator should perform the lesion counts and EGSS evaluations at all visits from baseline to week 12 for the same subject.

*Inflammatory lesions* are defined as follows:

Papule: An erythematous, raised, palpable lesion less than 5 mm in diameter

Pustule: An erythematous, raised, likely palpable lesion containing white exudate or pus less than 5 mm in diameter

Nodule: A deep-seated, erythematous, firm lesion greater than 5 mm in diameter

*Non-inflammatory lesions* are defined as follows:

Open comedone (blackhead): A widely dilated sebaceous follicle plugged with darkly pigmented sebum

Closed comedone (whitehead): A small, closed sebaceous follicle distended with sebum, with a white appearance

*Evaluator's Global Severity Score (EGSS)*

At each visit the severity will be determined based on evaluator-blinded evaluations of the signs and symptoms of acne vulgaris. Evaluations will be scored on a scale of 0-4, with 0 being clear and 4 being severe. Please see the table below for complete definitions.

Score	Grade	Description
0	Clear	Normal, clear skin with no evidence of acne vulgaris
1	Almost clear	Rare non-inflammatory lesions present, with rare non-inflamed papules (papules must be resolving and may be hyperpigmented, though not pink-red)

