## 8 Selection and Withdrawal of Subjects

### 8.1 Subject Inclusion Criteria

Subjects meeting all of the following criteria will be eligible for study entry:

1. Male or female at least 9 years of age and older;
2. Written and verbal informed consent must be obtained. Subjects less than age of consent must sign an assent for the study and a parent or a legal guardian must sign the informed consent (if subject reaches age of consent during the study they should be re-consented at the next study visit);
3. Subject must have a score of 3 (moderate) or 4 (severe) on the Evaluator's Global Severity Score (EGSS) assessment at the baseline visit;
4. Subjects with facial acne inflammatory lesion (papules, pustules, and nodules) count no less than 20 but no more than 50;
5. Subjects with facial acne non-inflammatory lesion (open and closed comedones) count no less than 25 but no more than 100;
6. Subjects with two or fewer facial nodules;
7. Females of childbearing potential and females who are pre-menses must be willing to practice effective contraception for the duration of the study. (Effective contraception is defined as stabilized on oral contraceptive for at least 3 months, IUD, condom with spermicidal, diaphragm with spermicidal, implant, Nuvaring, injection, transdermal patch, abstinence or sterile partner.) Females on hormonal contraceptive must have taken the same type for at least three months prior to entering the study and must not change type during the study. Those who have used hormonal contraception in the past must have discontinued usage at least three months prior to the start of the study. Women who use birth control for acne control only should be excluded.
8. Pre-menses females and females of childbearing potential must have a negative urine pregnancy test at the screening and baseline visits;
9. Subjects must be willing to comply with study instructions and return to the clinic for required visits. Subjects under the age of consent must be accompanied by the parent or legal guardian at the time of assent/consent signing;
10. If a cleanser, moisturizer or sunscreen is needed during the study, subjects must be willing to use only allowed cleansers, moisturizers, sunscreens, or

---

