#### Evaluations and Analyses

Inflammatory lesions and non-inflammatory lesions will be recorded for each subject at Baseline and at Weeks 2, 4, 8, and 12. The absolute and percent change from baseline of inflammatory lesions and non-inflammatory lesions will be derived for each subject at Weeks 2, 4, 8, and 12.

The EGSS will be recorded for each Subject. The EGSS will be dichotomized into “success” and “failure” at Week 2, 4, 8 and 12 with a subject considered a success for those visits if the EGSS is at least 2 grades less than baseline and are Clear or Almost Clear.

Subjects will be asked to complete the Acne-Specific Quality of Life Questionnaire at Baseline and Week 12.

All assessments will be conducted for both ITT and PP.

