#### **12.1.1 Primary Efficacy**

There are three co-primary efficacy endpoints:

- Absolute change in inflammatory lesion count from Baseline to Week 12
- Absolute change in non-inflammatory lesion count from Baseline to Week 12
- Percentage of subjects who achieve at least a two-grade reduction at Week 12 from Baseline in the Evaluator's Global Severity Score and were Clear or Almost Clear

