### 12.1.5 Test of Superiority for EGSS

The EGSS will be dichotomized into “success” and “failure” with a subject considered a success for those visits if the Evaluator’s Global Severity Score is at least 2 grades less than Baseline and are Clear or Almost Clear. The analysis of the dichotomized Evaluator’s Global Severity Score will be based on a logistic regression test with factors of treatment group and analysis center.

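### The EGSS success rule in the primary imputation step (Section 12.1.9, step 2) omits the 'at least' that defines the co-primary endpoint and should be aligned with it before unblinding

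*Combined protocol and SAP*

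**What the plan says.** The endpoint and its dichotomization are stated in full in five places, always with a minimum reduction:

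- Synopsis, co-primary efficacy: "Percentage of subjects who achieve at least a two-grade reduction from baseline and are Clear or Almost Clear at Week 12".
- Synopsis, statistical methods: the same two conditions, for each post-baseline visit.
- Section 12, Evaluations and Analyses: success if the "EGSS is at least 2 grades less than baseline and are Clear or Almost Clear".
- Section 12.1.1: "Percentage of subjects who achieve at least a two-grade reduction at Week 12 from Baseline", combined with Clear or Almost Clear.
- Section 12.1.5, which governs the EGSS test: success if the score "is at least 2 grades less than Baseline and are Clear or Almost Clear".

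Section 12.1.9 then sets out how missing EGSS values are handled. Step 1 fills in missing scores by MCMC within each arm. Step 2 derives success in each completed data set, just before the logistic regression: "the dichotomous success rate (clear or almost clear with a 2-point change from baseline) will be computed". Imputed Week 12 scores are first rounded to whole grades.

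Two other facts bear on the arithmetic. The scale runs over five grades: "Evaluations will be scored on a scale of 0-4, with 0 being clear and 4 being severe". Eligibility restricts the baseline grade: "Subject must have a score of 3 (moderate) or 4 (severe").

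**The concern.** Step 2 is worded as a computing instruction for the primary analysis, and its responder threshold is not the one in the endpoint definition. A two-point change and a change of at least two grades differ for any subject who improves by three or four grades. Those are the subjects who reach Clear from grade 3 and all subjects with severe acne who respond.

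The endpoint is one of three co-primaries that must all be significant (Sections 12.1.6 and 12.8.5), and failure on one also invalidates the secondary endpoints. If the step were programmed as written, the best responders would be scored as failures. The sensitivity analyses in Section 12.1.10, if they used the Section 12.1.5 rule, would then be testing a different endpoint from the primary analysis. If the discrepancy were noticed only after unblinding, the definition of a co-primary would have to be settled with the results in view.

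**Working it through.** **1. Compare the two rules grade by grade.** Baseline can be 3 or 4 only. Scores of 0 and 1 are the only ones that count as Clear or Almost Clear.

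| Baseline to Week 12 | Change | Sections 12.1.1 and 12.1.5 (at least 2) | Step 2 read as exactly 2 |
|---|---|---|---|
| 3 to 0 | 3 | success | failure |
| 3 to 1 | 2 | success | success |
| 4 to 0 | 4 | success | failure |
| 4 to 1 | 3 | success | failure |
| 3 to 2 | 1 | failure | failure |
| 4 to 2 | 2 | failure (Mild) | failure (Mild) |

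Outcomes of 3 or 4 fail under both rules. Under the literal reading the only success is 3 to 1. For a grade 4 subject the two conditions cannot both hold, because 4 − 2 = 2, which is Mild. The subgroup summary of dichotomized EGSS by baseline severity (Section 12.1.11) would then show 0% in both arms for severe subjects, by construction.

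Because baseline is 3 or 4, reaching 0 or 1 already implies a drop of at least two grades. The change clause in step 2 therefore alters the result only if it is read as exactly two.

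**2. Reproduce the plan's own figure.** Inputs from Section 12.8.2: 26.6% v 14.3%, two-sided alpha 0.05, power 95%, equal allocation. The mean rate is p̄ = 0.2045 and the difference is d = 0.123.

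- Uncorrected: n = [1.960·√(2p̄(1−p̄)) + 1.645·√(p1(1−p1)+p2(1−p2))]² / d² = 276.5.
- Continuity-corrected: (n/4)·[1 + √(1 + 4/(n·d))]² = 292.5, which rounds up to 293 per arm. This is the plan's figure exactly.

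**3. Power at 300 per arm under the defined endpoint.** With N = 300 per arm,

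power = Φ{ [√N·(d − 1/N) − 1.960·√(2p̄(1−p̄))] / √(p1(1−p1)+p2(1−p2)) }

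= Φ{ (2.073 − 1.118) / 0.5637 } = Φ(1.694) = 95.5%.

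**4. Illustrate the effect of literal coding.** Let f be the share of true successes that are not 3 to 1. The documents do not give f. It is assumed here and, in this table, taken as equal in both arms, so each rate is multiplied by (1 − f). For f = 10%: Φ{(1.860 − 1.074)/0.5424} = Φ(1.448) = 92.6%. For f = 30%: Φ{(1.434 − 0.971)/0.4915} = Φ(0.942) = 82.7%.

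| f (assumed) | Rates | Power, corrected | Power, uncorrected |
|---|---|---|---|
| 0 | 26.6% v 14.3% | 95.5% | 96.4% |
| 5% | 25.3% v 13.6% | 94.2% | 95.3% |
| 10% | 23.9% v 12.9% | 92.6% | 94.0% |
| 20% | 21.3% v 11.4% | 88.5% | 90.5% |
| 30% | 18.6% v 10.0% | 82.7% | 85.5% |
| 40% | 16.0% v 8.6% | 75.0% | 78.8% |

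If the active arm lost more than vehicle, say 20% v 10% (21.3% v 12.9%, again assumed), power would be 75.0% corrected and 78.3% uncorrected. These are simple two-proportion calculations. They ignore the analysis-center factor and the imputation variance in the planned model.

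**The case against.** The strongest reply is that nothing in step 2 says 'exactly'. Section 12.1.9 is about missing data, and its introduction refers to the dichotomized EGSS as something already defined. Five full statements, including the one governing the test in Section 12.1.5, give the minimum reduction. The exact reading would bar success for every severe subject the trial sets out to enroll, and would make a planned subgroup summary meaningless. Section 12.8.2 drops 'at least' in the same way, one sentence after stating it in full, and nobody would take that as a new endpoint. Section 12 also promises a separate SAP before unblinding, which may state the rule correctly; the text available here does not allow a check.

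Most of this stands. It makes shorthand the likely intent and literal coding unlikely. It does not make the phrase correct: Section 12.8.2 describes planning rates, whereas step 2 tells a programmer what to compute for a co-primary endpoint.

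A reader might infer three stronger things that the documents do not support:

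- *That step 2 is the only operational derivation of success.* Sections 12 and 12.1.5 also state the dichotomization rule.
- *That every analysis data set is affected.* Step 2 covers the completed data sets of the primary MCMC analysis, observed values included. In Section 12.1.10 the repeated-measures logistic model uses no imputation, and the model-based method imputes the already dichotomized outcome. Neither is said to pass through step 2.
- *That the trial is underpowered.* The loss requires literal coding and a share of affected successes that is not given. Without the continuity correction, power stays above 95% when 5% of successes are lost.

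**Conclusion.** The wording conflict is real and sits in the derivation step of a co-primary analysis. It is an inconsistency of text, not evidence that the intended endpoint is wrong. The grade arithmetic is certain once the clause is read as exactly two: one success path of four remains, and none for severe subjects. The consequence for power is conditional and cannot be sized from the documents. The illustration of about 93% at 10% lost and 83% at 30% lost, against 95.5%, assumes literal coding, equal loss in both arms, 300 per arm and the plan's own continuity-corrected method. The text should be corrected because it sets a responder threshold in the primary analysis and the correction is trivial. The design and sample size need no change on this account.

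**What to change.** Before unblinding, replace the parenthetical in Section 12.1.9, EGSS step 2, with: *EGSS of 0 or 1 at Week 12 and a reduction of at least 2 grades from Baseline, as defined in 12.1.1 and 12.1.5*. Use the same definition in the derivation specification and in all the EGSS sensitivity analyses of Section 12.1.10, including the tipping point analysis, so that primary and sensitivity results refer to one endpoint.

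The cost is one phrase in the protocol or the separate SAP. No data collection, sample size or subject is affected.
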